**Table 1. Study Schedule**

Visit	SCRN	Treatment Period							EOT/DC	Post-Tx F/U	Survival F/U
		Cycle 1			All subsequent Cycles						
Visit date	≤ 28	≤ 14	1 (BSLN)	15	29*	1*	15	29	-	EOT + 28 days	-
Visit window	-	-	-	± 3 days				± 7 days			
Informed consent	X										
Demography	X										
Medical history 	X										
GC history 	X										
Height & weight 		X	X ¥	X		X ¥	X		X	X	
Physical examination		X	X ¥	X		X ¥	X		X	X	
Vital signs 		X	X ¥	X		X ¥	X		X	X	
ECOG performance		X	X ¥	X		X ¥	X		X	X	
12-lead ECG		X	X ¥20	X 		X ¥20			X	X	
Chest X-ray			As clinically indicated								
Hematology 		X		X		X ¥	X		X	X	
Blood chemistry 		X		X		X ¥	X		X	X	
Coagulation tests 		X		X		X ¥	X		X	X	
Urinalysis 		X		X		X ¥	X		X	X	
Pregnancy test 		X	As clinically indicated or per local regulatory requirement 								
Serological test 		X									
QOL 			X ¥			X ¥			X		
CT (or PET-CT) or MRI		X						X 	X 		

Visit	SCRN		Treatment Period						EOT/DC	Post-Tx F/U	Survival F/U
			Cycle 1			All subsequent Cycles					
Visit date	≤ 28	≤ 14	1 (BSLN)	15	29*	1*	15	29	-	EOT + 28 days	-
Visit window	-	-	-	± 3 days					± 7 days		
Biopsy 	As clinically indicated										
Eligibility review		X									
Randomization			X								
IP administration (qd)			X	X	X	X	X	X			
Adverse Events 	X	X	X	X	X	X	X	X	X	X	
Previous/Concomitant Medication 	X	X	X	X	X	X	X	X	X	X	
PD markers 			X ¥			X ¥			X		
PK sampling 			X	X		X					
Survival F/U 											X

1 cycle = 28 days, SCRN, Screening; BSLN, Baseline; W, Week; wks, weeks; EOT, End of Treatment; F/U, Follow-Up; Tx, Treatment; DC, Discontinuation; EOS, End of Study

\*Note: Typically, Day 29 evaluations (adverse events and concomitant medication) of each cycle will not require a clinic visit and will not be performed if the patient is returning for Day 1 of the next cycle within the visit window (+ or - 3 days).

¥Procedures should be performed before IP administration on the day of start.

- 1) Medical history within 1 year (within 3 years for cancer) from signing on the ICF should be collected. Medical history includes clinically significant past and current diagnosis including surgical procedures. Any surgical procedures done for treatment of GC will be collected separately regardless when those were carried out.
- 2) Full history of GC including date of initial diagnosis, primary location ([≥ 5 cm below GEJ] vs. GEJ), stage, metastatic and prior treatment information should be collected.
- 3) Height is measured once at Screening visit.

- 4) Vital signs include weight, sitting systolic/diastolic blood pressure, heart rate, respiration rate, and body temperature.
- 5) Hematology test (complete blood count, CBC) to be performed locally must include white blood cell (WBC) with 5-part differential (neutrophils, lymphocytes, monocytes, eosinophils, and basophils), platelet count, absolute neutrophil count (ANC), red blood cell (RBC), hemoglobin (Hb), and hematocrit (Hct). If hematological treatment related toxicity occurs, the hematological test can be performed more frequently at the investigator's discretion during the treatment period.
- 6) Chemistry test to be performed locally must include sodium, potassium, chloride, carbon dioxide or bicarbonate (if required), blood urea nitrogen (BUN), creatinine, glucose (Fasting glucose at the Screening visit. Further fasting glucose only if necessary in the opinion of the investigator), total protein, albumin, calcium, amylase, lipase, phosphorous, magnesium, creatinine kinase (CK), uric acid, total bilirubin, AST, ALT, and ALP. If non-hematological treatment related toxicity occurs, the chemistry test can be performed at the investigator's discretion during the treatment period.
- 7) Coagulation test to be performed locally includes prothrombin time expressed as either prothrombin time (PT) or international normalized ratio (INR) and partial thromboplastin time (PTT or aPTT).
- 8) Urinalysis test to be performed locally includes specific gravity, protein, glucose, occult blood, and, only if indicated, with microscopic examination.
- 9) This will be ordered only for women of child-bearing potential (serum or urine) including women who have not been surgically sterile, or post-menopausal for at least 1 year prior to Screening visit (no other medical cause involved).
- 10) Additional pregnancy test may be performed if required by local health authorities. Additional pregnancy test is required at the beginning every treatment cycle, and at EOT visit for Germany and Romania. Additional pregnancy test is required at the beginning of every treatment cycle, at EOT visit, and at post-treatment follow-up visit for Poland.
- 11) Serological tests to be performed locally include HIV antibody (if HIV antibody result is positive, HIV-1 antibody and HIV-2 antibody should be conducted), HBs antigen, and HCV antibody.
- 12) Subjects will complete two questionnaires; EORTC-QLQ-30 with EORTC QLQ-STO22 and EQ-5D-5L at baseline and then approximately every 4 weeks typically either at the end of the cycle or at the beginning of the next cycle.
- 13) Tumor will be assessed based on chest, abdominal and pelvic CT (or PET-CT) scan or MRI approximately every 8 weeks at the end of every other cycle. The same method should be used for the assessment of tumor response throughout the study. RECIST Guideline Version 1.1 will be used to assess tumor response. CT (or PET-CT) scan/MRIs after Baseline are allowed to perform within 7 days prior to the planned visit date. Scans to confirm progression of disease or for other reasons not per schedule as determined by the investigator may be performed when needed.
- 14) If a diagnosis cannot be made with chest, abdominal and pelvic CT (or PET-CT)/MRI due to atypical radiological appearance, primary or metastatic biopsy is recommended. Subsequent biopsies are carried out based on the investigator's discretion but it should be considered in case of growth or change in the enhancement pattern identified during follow-up. Histopathologic examination of the biopsy specimen should be assessed by an expert pathologist.

- 15) Adverse events will be documented for any untoward medical occurrence in a patient from the time they sign the informed consent form and until study completion per the Study Schedule.
- 16) Any medications administered within 28 days prior to signing the ICF and current medications should be collected. Medications for treatment of GC will be collected separately regardless when those were administered.
- 17) PD markers include vascular endothelial growth factor (VEGF), sVEGFR-1, sVEGFR2 and sVEGFR3.
- 18) PK sampling will be performed once prior to dosing on Day 1 of every cycle until EOT and at further timepoints on Day 1 of Cycle 1 and Day 15 of Cycle 1. Details are provided in [Section 5.4.4](#) and in the PK Sampling Manual.
- 19) Subjects who prematurely discontinue study treatment but who are not withdrawn from the study will be followed every 8 weeks ( $\pm$  7 days) for tracking of their survival until death or the end of the study. This survival follow-up should be performed via telephone, certified letter or during subjects' visit to the investigational site or other clinic site where confirmation of survival information documentation can be obtained. In addition, publicly accessible data may be used to document death. More frequent follow-up may be necessary at the time of the interim and final analysis to provide the most up-to-date survival information.
- 20) 12-lead ECG will be performed within 14 days before the date of randomization, at Day 1 of every cycle (before IP administration), at EOT visit and at the post-treatment follow-up visit. In addition to this, 12-lead ECG should be performed approximately 4 hours after IP administration on Cycle 1 Day 1 and Cycle 1 Day 15 corresponding to the same time when the PK  $C_{max}$  blood is drawn.

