### 3.4.1. Screening Visit

Upon signing on the informed consent form, the screening period will start. Screening should be completed within 28 days before the date of randomization. Within this period, following procedures are to be carried out. Any procedures or assessments associated with the study should be initiated only after obtaining the written informed consent from potential subjects. If procedures within the 28-day window were performed as part of standard of care prior to consent, those evaluations may be used as screening period results.

- Informed consent
- Collection of demographic information
- Collection of medical history
- Collection of GC history
- Collection of previous/concomitant medication information
- Assessment of adverse events

 In Japan, when the patient is under 20 years old, informed consent will be obtained from both the patient and the legal guardian.

 Medical history within 1 year (within 3 years for cancers) from signing on the ICF should be collected. Medical history includes clinically significant past and current diagnosis including surgical procedures. Any surgical procedures done for treatment of GC will be collected separately regardless when those were carried out.

 Full history of GC including date of initial diagnosis, primary location ( $\geq 5$  cm below GEJ) vs. GEJ), stage, and metastatic information should be collected.

 Any medications administered within 28 days from signing the ICF and current medications should be collected. Medications for treatment of GC will be collected separately regardless of when those were administered.

 Any untoward medical occurrence in a patient who has signed the informed consent form will be collected as an adverse event.

The following should be completed within 14 days before the baseline visit. These data except vital signs, which will be measured again in the baseline visit, will be used as baseline data for determination of eligibility of subjects in the study.

- Measurement of height
- Physical examination
- Measurement of vital signs including weight

- Assessment of ECOG performance score
- 12-lead ECG
- Hematology, blood chemistry, serological test, coagulation test and urinalysis
- Pregnancy test
- CT/MRI for GC evaluation
- Biopsy for GC evaluation

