#### **4.3. Administration of Investigational Product**

Investigational products will be administered orally once a day, approximately 1 hour after breakfast. It is recommended that the administration time should be consistent throughout the study period (that is, the administration interval should be approximately 24 hours). The investigational product should not be taken until during the clinic visit of Day 1 of each cycle.

Subjects should take 3 tablets of 200 mg and 1 tablet of 100 mg in strength at a time. If the dose is reduced to 600 mg, 3 tablets of 200 mg in strength should be taken. If the dose is reduced further to 400 mg, only 2 tablets of 200 mg in strength should be taken at a time. If the subject vomits after swallowing the IP, the dose will not be replaced and there will be no replacement of a missed dose of IP.

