### 5.3.2. Clinical Laboratory Tests

The following tests will be performed locally at individual investigational sites. Hematology, chemistry, coagulation and urinalysis will be performed at Day 1 (before IP administration) and Day 15 of every cycle, the end of treatment (EOT) visit and the post-  
tx F/U visit. If hematological or non-hematological treatment related toxicity occurs, laboratory tests can be performed at the investigator's discretion during the treatment period. Serological tests will be performed only at the screening visit and additional tests can be performed as clinically indicated or as required by local health authorities.

- Hematology (complete blood count, CBC: white blood cell (WBC) with 5-part differential (neutrophils, lymphocytes, monocytes, eosinophils, and basophils), platelet count, absolute neutrophil count (ANC), red blood cell count (RBC), hemoglobin (Hb), hematocrit (Hct)
- Blood chemistry: sodium, potassium, chloride, carbon dioxide or bicarbonate (if required), blood urea nitrogen (BUN), creatinine, glucose (fasting), total protein, albumin, calcium, amylase, lipase, phosphorous, magnesium, creatinine kinase (CK), uric acid, total bilirubin, AST, ALT, and ALP
- Serological tests: HIV antibody (if HIV antibody result is positive, HIV-1 antibody and HIV-2 antibody should be conducted), HBs antigen, HBs antibody, HBC antibody, HCV antibody
- Coagulation tests: prothrombin time expressed as either prothrombin time (PT) or international normalized ratio (INR) and partial thromboplastin time (PTT or aPTT)
- Urinalysis: specific gravity, protein, glucose, occult blood, and microscopic examination if indicated
- Pregnancy test: it will be carried out only for female subjects with child-bearing potential (serum or urine).

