8.3 Clinical Laboratory Evaluation

Laboratory data will be classified according to CTC Grade (NCI-CTCAE version 4.03). A shift table from baseline to worst NCI-CTC grade will be presented.

- *Table. Shift from Baseline of Hematology Tests by Worst NCI-CTC Grade: Rivoceranib + BSC [Parameter] – Safety Set*
- *Table. Shift from Baseline of Hematology Tests by Worst NCI-CTC Grade: Placebo + BSC [Parameter] – Safety Set*
- *Table. Shift from Baseline of Blood Chemistry Tests – serum electrolyte by Worst NCI-CTC Grade: Rivoceranib + BSC [Parameter] – Safety Set*
- *Table. Shift from Baseline of Blood Chemistry Tests – serum electrolyte by Worst NCI-CTC Grade: Placebo + BSC [Parameter] – Safety Set*
- *Table. Shift from Baseline of Blood Chemistry Tests – liver enzymes by Worst NCI-CTC Grade: Rivoceranib + BSC [Parameter] – Safety Set*
- *Table. Shift from Baseline of Blood Chemistry Tests – liver enzymes by Worst NCI-CTC Grade: Placebo + BSC [Parameter] – Safety Set*
- *Table. Shift from Baseline of Blood Chemistry Tests – others by Worst NCI-CTC Grade: Rivoceranib + BSC [Parameter] – Safety Set*
- *Table. Shift from Baseline of Blood Chemistry Tests – others by Worst NCI-CTC Grade: Placebo + BSC [Parameter] – Safety Set*

- *Table. Shift from Baseline of Coagulation Tests by Worst NCI-CTC Grade: Rivoceranib + BSC [Parameter] – Safety Set*
- *Table. Shift from Baseline of Coagulation Tests by Worst NCI-CTC Grade: Placebo + BSC [Parameter] – Safety Set*

To investigate a normal/abnormal shift from baseline by visit, results will be classified as Normal, Abnormal NCS, or Abnormal CS and presented with a shift table. Subjects who were 'Normal' or 'Abnormal - not clinically significant (NCS)' at baseline but shifted to 'Abnormal - clinically significant (CS)' will be summarized in the following tables and listings. Significant shift from baseline will be tested using McNemar's or Bowker's test.

- *Table. Shift from Baseline of Hematology Tests [Parameter] – Safety Set*
- *Table. Shift from Baseline of Blood Chemistry Tests – serum electrolyte [Parameter] – Safety Set*
- *Table. Shift from Baseline of Blood Chemistry Tests – liver enzymes [Parameter] – Safety Set*
- *Table. Shift from Baseline of Blood Chemistry Tests – others [Parameter] – Safety Set*

- *Table. Shift from Baseline of Coagulation Tests [Parameter] – Safety Set*

- *Table. Shift from Baseline of Urinalysis Tests [Parameter] – Safety Set*

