10.5 Baseline

Baseline is defined as the value at Cycle 1 Day 1, or the last value observed prior to randomization if this is not available.

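### Glucose must be fasting only at screening under Table 1, yet the SAP labels every value fasting and tests shifts from baseline within each arm, so fasting status alone can produce a significant shift

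*Protocol*

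**What the plan says.** **Fasting rule.** Footnote 6 to Protocol Table 1 reads: "Fasting glucose at the Screening visit. Further fasting glucose only if necessary in the opinion of the investigator". The corresponding footnote to Table 2 (extension period) says the same. Protocol 5.3.2 lists the analyte as "creatinine, glucose (fasting), total protein", with no limit by visit, and SAP 5.9.8 uses the same label.

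**Sampling times.** Protocol 5.3.2 says: "Hematology, chemistry, coagulation and urinalysis will be performed at Day 1 (before IP administration) and Day 15 of every cycle". Table 1, however, has no chemistry at Cycle 1 Day 1, and neither does the list of baseline-visit procedures in Protocol 3.4.2. Chemistry appears in Table 1 at screening, Cycle 1 Day 15, Days 1 and 15 of later cycles, end of treatment and post-treatment follow-up.

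**Baseline.** SAP 10.5: "Baseline is defined as the value at Cycle 1 Day 1, or the last value observed prior to randomization if this is not available". Protocol 3.4.1 says of the screening assessments: "These data except vital signs, which will be measured again in the baseline visit, will be used as baseline data". It adds that this is for determining eligibility.

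**Analysis.** SAP 8.3: "A shift table from baseline to worst NCI-CTC grade will be presented", one table per arm. It also classifies results as normal, abnormal not clinically significant (NCS) or abnormal clinically significant (CS), tabulates shifts from baseline by visit, and tests them with McNemar's or Bowker's test. The heading of SAP 14.2 places this test within treatment group; the body of that section is redacted.

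**Food and dosing.** Protocol 4.3: "Investigational products will be administered orally once a day, approximately 1 hour after breakfast".

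**The concern.** A paired shift test assumes that the two members of each pair were measured in the same way. If the baseline glucose is fasting and the follow-up glucose may be fed, the test picks up the change in sampling conditions together with any drug effect. A within-arm test has no control term, so an equal meal effect in the placebo arm is not subtracted.

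Because the SAP calls all the values fasting, a reader of the safety report would have no reason to suspect this. At stake is a p-value for one analyte that could be read as a metabolic effect of the drug when it reflects only how the blood was taken.

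**Working it through.** The plan states no figure on this point, so there is none to reproduce. The check has two parts.

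**1. Which reading of the protocol exposes the test?**

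| Chemistry at Cycle 1 Day 1? | Fasting rule followed | SAP baseline | Later values | Like with like? |
|---|---|---|---|---|
| No (Table 1, 3.4.2) | Footnote 6 | Screening, fasting | Uncontrolled | No |
| No (Table 1, 3.4.2) | 5.3.2 label | Screening, fasting | Fasting | Yes |
| Yes (5.3.2) | Footnote 6 | Cycle 1 Day 1, uncontrolled | Uncontrolled | No systematic difference built in |
| Yes (5.3.2) | 5.3.2 label | Cycle 1 Day 1, fasting | Fasting | Yes |

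The first row is what a site does if it follows Table 1 and its own footnote throughout, which is a legitimate reading. Fed samples are plausible there. The dose is taken about an hour after breakfast, and Day 1 chemistry of later cycles is drawn before the dose at the clinic, so a draw between breakfast and dose fits the schedule. Day 15 chemistry carries no pre-dose mark in Table 1.

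**2. Could a modest artefact reach significance?**

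Inputs from the documents:
- About 459 subjects (Protocol Synopsis), randomized 2:1 (Protocol 4.2): 459 × 2/3 = 306 and 459 × 1/3 = 153.
- Two-sided 5% level (SAP 10.1).

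Inputs assumed, because the documents give no glucose data:
- A proportion u moves from normal to abnormal because of fasting status; a proportion d = 3% moves back.
- No drug effect.
- Two categories instead of the SAP's three.
- Every randomized subject has a pair at the visit tested.

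Method: exact two-sided McNemar test. The number of discordant pairs m is binomial (n, u + d). Given m, the number moving up is binomial (m, u/(u + d)). The probability of significance is summed over all outcomes whose exact p-value, from a binomial (m, 1/2), is at most 0.05.

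| u | d | n = 306 | n = 153 |
|---|---|---|---|
| 3% | 3% | 2.9% | 2.1% |
| 5% | 3% | 17% | 8% |
| 8% | 3% | 71% | 38% |
| 10% | 3% | 92% | 62% |
| 15% | 3% | >99% | 94% |

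The first row is the calibration check: with no artefact, the exact test stays below 5%.

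A hand check of the 8% row uses the usual statistic (b − c)²/(b + c) at the expected counts:
- n = 306: b = 24.48, c = 9.18, giving 15.3²/33.66 = 6.95.
- n = 153: b = 12.24, c = 4.59, giving 7.65²/16.83 = 3.48.

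The 5% critical value is 1.96² = 3.84, so the larger arm passes and the smaller one just misses. The same artefact can therefore look significant on drug and not on placebo because of the 2:1 allocation alone. Halving n takes 71% to 38%, which also shows how the risk falls at later visits as subjects leave.

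**The case against.** The strongest reply is that the artefact is conditional. Footnote 6 permits non-fasting samples but does not require them, and nothing says that breakfast comes before the blood draw. If sites follow 5.3.2, every value is fasting and the problem disappears. That stands: a reader might infer that a fed-state rise will be reported as a worsening, but the documents support only that it can be.

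Second, SAP 8.3 does not name glucose among its tables; it presumably falls under the blood chemistry category for other parameters. The mock tables are only listed and the body of SAP 14.2 is redacted, so a fasting flag or exclusion may exist out of sight. This limits how firmly the point can be put. It does not remove the conflict between the visible passages.

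Third, investigators can class a fed value as NCS. That keeps the subject off the listing of shifts to CS, but a move from normal to NCS still enters the tested table.

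Fourth, the trial is blinded and placebo-controlled, so a meal effect should appear in both arms and be visible to a careful reader. This is a fair defence of a side-by-side description. It does not defend a p-value computed within one arm.

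A reader might also infer that the worst-grade tables will favour placebo, because the arm treated longer is sampled more often and has more chances to cross a grade. That should not be part of this point. It applies to every laboratory parameter, has nothing specific to do with fasting, and would not be cured by controlling fasting. Any size put on it would rest on assumed crossing rates, independent repeat samples, and progression-free survival medians from an earlier trial used as time on treatment.

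**Conclusion.** The inconsistency is real, and it leaves one planned test exposed. On the Table 1 schedule, SAP 8.3 would compare a fasting baseline with follow-up values of unknown fasting status and present the result as a like-for-like shift.

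Under assumed rates of 8% and 3% with no drug effect, the within-arm test is significant in about 71% of trials at 306 subjects and 38% at 153. Across assumed upward rates of 5% to 15%, the range is 17% to over 99% at 306 and 8% to 94% at 153. These figures rest on the assumed rates, on two categories instead of three, and on all randomized subjects being paired. The last assumption makes them upper values for any given pair of rates, since the test is run by visit and numbers fall over time.

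The importance is low. One safety analyte is involved, no efficacy result is touched, and a comparison of drug with placebo is not obviously biased.

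**What to change.** - **Reconcile the passages.** Bring footnote 6 (and its copy in Table 2) into line with Protocol 5.3.2 and SAP 5.9.8, both on when glucose is fasting and on whether chemistry is drawn at Cycle 1 Day 1.
- **Record fasting status** with each glucose sample, if the laboratory page does not already do so.
- **SAP 8.3, one sentence:** the within-arm shift test is not applied to glucose unless the baseline and follow-up samples have the same recorded fasting status.
- **Present glucose grades descriptively**, both arms side by side and labelled by fasting status, keeping the non-fasting values.

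Grading only the fasting samples is a tempting alternative but a poor one. Under footnote 6, later fasting draws happen when the investigator thinks them necessary, so the retained values would be selected by clinical suspicion and most routine follow-up could be lost.

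The cost is one fewer p-value for one analyte and one flag on the laboratory page. If fasting status was not recorded, the test is omitted for glucose and the tables state that fasting status is unknown.
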